10.5 Safety Monitoring

All study participants who receive treatment will be assessed for the occurrence of treatment related adverse events. Adverse events of potential concern related to the vaginal packing, are acute vaginal adverse events (aVAE) which: i) is determined to be at least possibly related to BrachyGel; ii) occurs within the first 30 days from 1st Brachytherapy treatment utilizing BrachyGel (ie. Period 2 or 3 depending on the randomization arm); and iii) meets the criterion below:

Has any of the following vaginal toxicities grade >= 3 according to CTCAE:

- Vaginal pain
- Vaginal perforation
- Vaginal hemorrhage
- Vaginal inflammation
- Vaginal infection
- Dyspareunia

Safety will be assessed by monitoring the number of participants who experience an aVAE. Results reported in Romano et al 2017 on high-dose brachytherapy experience at UVA noted that 0/74 = 0% (upper limit of 95% CI of 4.9%) patients experienced grade ≥3 aVAE.²⁰ Others have reported similarly low rates with at most 2% for late vaginal toxicity.^{21,22} For this study the upper boundary of a sequential probability ratio test (SPRT) based upon a binomial test of proportions for aVAE will be used for monitoring, to protect against excessive aVAE rates. The stopping boundary is for a SPRT contrasting a null 4% versus an unacceptable 9% aVAE rate, with nominal type I and II errors of 10% and 10%, respectively. The slope of the parallel line for monitoring is 2.54 and the intercept is 0.062.

Safety stopping guidelines for the occurrence of aVAEs are detailed in the following table. If a stopping bound is crossed then accrual to the study will be suspended until the study PI, co-investigators and the DSMC can review the data, and determine if the study should continue, be amended or be closed to further accrual.

| Number of participants who received BrachyGel | Number with grade ≥ 3 aVAE | | |
|---|----------------------------|--|--|
| 3-7 | ≥ 3 | | |
| 8-23 | ≥ 4 | | |
| 24-39 | ≥ 5 | | |
| 40-45 | ≥ 6 | | |

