| | To estimate the difference in physician-scored use experience between BrachyGel and standard vaginal packing. | Physician-scored use experience scored on a 4-point scale for periods 1 through 4 (e.g. fractions 2 through 5). |
| Study Population: | Adult women with locally advanced cervical cancer (FIGO Stages IB1-IVB) for whom brachytherapy boost is planned using intracavitary high-dose rate brachytherapy as part of definitive radiation therapy. | |
| Description of Sites/Facilities Enrolling Participants: | Participants will be enrolled at the University of Virginia and at the Allegheny Health Network | |
| Description of Study Intervention: | Participants will receive brachytherapy according to clinical care and will alternate between standard packing and BrachyGel packing. The order of alternation will vary between Arms A and B. | |
| Study Duration: | Accrual should be completed within 14 months and data collection and analysis will take after 12 additional months (total of 26 months). | |

| Participant Duration: | Each participant will receive 5 fractions of brachytherapy, each about |
|-----------------------|--|
| | 2-7 days apart, followed by a 30 day safety visit. |
| | |

Version Date: 11/16/2021

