4 STUDY DESIGN

4.1 Overall Design

This is a two-center, stratified and randomized, four period, two arm crossover, non-inferiority trial to demonstrate that BrachyGel Vaginal Hydrogel Packing System is non-inferior to standard method vaginal packing (standard).

Two sites are included in the trial design in order to reflect the most common applicators used in intracavitary cervical cancer brachytherapy:

- Tandem and ovoid brachytherapy+/- interstitial needles (UVA cohort)
- Tandem and ring-based brachytherapy +/- interstitial needles (AHN cohort)

The BrachyGel Hydrogel Vaginal Packing System will be compared to gauze packing and/or rectal retractor packing per the institution's standard of care packing practice.

Participants will be stratified by site (UVA/AHN) and randomized to either Arm A or Arm B. Fraction 1 for all participants (both Arms) will be according to standard of care packing and fractions 2-5 (periods 1-4) will alternate between standard of care and BrachyGel packing, as shown in *Figure 1*.

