6 STUDY INTERVENTION

6.1 Description of Study Intervention(s)

Participants will be assigned to Arm A or Arm B, as described in section 4.1 and Figure 1. Fraction 1 for all participants (both Arms) will receiving standard of care packing. During fractions 2-5 of brachytherapy, participants will have vaginal packing alternating between the BrachyGel Vaginal Hydrogel Packing System and standard of care vaginal packing, strategy which will include gauze vaginal packing or rectal retractor.

For Arm A of the study, the BrachyGel Packing System will be used during fractions 3 and 5. Standard packing will be used for fractions 1, 2 and 4.

For Arm B of the study, the BrachyGel Packing System will be used during fractions 2 and 4. Standard packing will be used for fractions 1, 3 and 5.

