9.1.5 Time Period and Frequency for Event Assessment and Follow-Up

The occurrence of an adverse event (AE) or serious adverse event (SAE) may come to the attention of study personnel during study visits and interviews of a study participant presenting for medical care, or upon review by a study monitor.

All AEs including local and systemic reactions not meeting the criteria for SAEs will be captured on the appropriate case report form (CRF). Information to be collected includes event description, time of onset, clinician's assessment of severity, relationship to study product (assessed only by those with the training and authority to make a diagnosis), and time of resolution/stabilization of the event. All AEs occurring while on study must be documented appropriately regardless of relationship. All AEs will be followed to adequate resolution.

Any medical condition that is present at the time that the participant is screened will be considered as baseline and not reported as an AE. However, if the study participant's condition deteriorates at any time during the study, it will be recorded as an AE.

Changes in the severity of an AE will be documented to allow an assessment of the duration of the event at each level of severity to be performed. AEs characterized as intermittent require documentation of onset and duration of each episode.

Version Date: 11/16/2021

Study staff will record all reportable events with start dates occurring any time after brachytherapy fraction 2 is completed until 30 days (for non-serious AEs) or anytime (for SAEs considered related to the study intervention) after the last day of study treatment. At each study visit, the investigator will inquire about the occurrence of AE/SAEs since the last visit. Events will be followed for outcome information until resolution or stabilization.

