10.3.2 Study Outcomes & Endpoints

Study measurements will be captured post each fraction of treatment. Assessments may include:

- Adverse events
- Dosimetry
- Physicist evaluation of imaging/packing
- Physician evaluation of imaging/packing
- Participant discomfort survey

There are two primary endpoints based upon dosimetry measurements in the bladder and the rectum. Each endpoint is the difference between D2cc dosimetry measurements obtained during periods 1 and 2 (fractions 2 and 3 under the 2x2 crossover structure). Additional assessments include data from periods 3 and 4 (fractions 4 and 5).

Additional endpoints include measurements over all periods for:

- Bladder and rectal dosimetry as measured by D0.1 cc and D1 cc.
- Participant reported discomfort
- Physicist evaluated imaging properties
- Physician evaluated imaging properties
- Physician evaluated use experience

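### The aVAE definition behind the safety stopping rule misnumbers the first BrachyGel period, and its 30-day window leaves only 16–26 counted days after the second BrachyGel use

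*Combined protocol and SAP*

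**What the plan says.** **The counted event (section 10.5).** An aVAE is a listed vaginal toxicity of grade ≥3, at least possibly related to BrachyGel, that "occurs within the first 30 days from 1st Brachytherapy treatment utilizing BrachyGel (ie. Period 2 or 3 depending on the randomization arm"). The number of participants with such an event is compared with the upper boundary of a sequential probability ratio test (SPRT), tabulated up to 45 participants who received BrachyGel. Crossing it suspends accrual pending review.

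**Period numbering.** Section 4.1 states that "fractions 2-5 (periods 1-4) will alternate between standard of care and BrachyGel packing". Section 10.3.2 agrees, describing the primary measurements as "obtained during periods 1 and 2 (fractions 2 and 3 under the 2x2 crossover structure").

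**Allocation (section 6.1).** "For Arm A of the study, the BrachyGel Packing System will be used during fractions 3 and 5". "For Arm B of the study, the BrachyGel Packing System will be used during fractions 2 and 4".

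**Spacing (section 1.1).** Fractions are "2-7 days apart, followed by a 30 day safety visit". Section 6.2.1 leaves delays to institutional guidelines and sets no limit.

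**Event recording (section 9.1.5).** Events are recorded if they start "any time after brachytherapy fraction 2 is completed until 30 days (for non-serious AEs") after the last day of study treatment. Related serious events are recorded with no end date.

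**The concern.** Two things in criterion ii) do not fit the rest of the protocol.

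First, the parenthesis disagrees with the words it explains. In Arm B, a treatment cannot be both the first BrachyGel use and in Period 3. Someone coding the count from the period label would start Arm B's clock at its second exposure.

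Second, each participant is scheduled for BrachyGel twice, but the clock is tied to the first use. The second exposure therefore gets less counted follow-up than the first, and less than the protocol already collects. An event can be recorded, graded 3 or higher, attributed to BrachyGel and still not count.

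This matters because the SPRT is the plan's only numerical stopping rule for vaginal toxicity, and section 2.2.5 says the device has not been used in living humans. Any uncounted event lowers the chance that the rule triggers.

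**Working it through.** **1. Period label.** Sections 4.1 and 10.3.2 give period = fraction − 1. Applied to section 6.1:

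| Arm | First BrachyGel | Second BrachyGel |
|---|---|---|
| A | fraction 3 = Period 2 | fraction 5 = Period 4 |
| B | fraction 2 = Period 1 | fraction 4 = Period 3 |

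First use is therefore Period 1 or 2. The printed pair, 2 or 3, matches the fraction numbers, so fractions were probably written as periods. In Arm B, Period 2 uses standard packing and Period 3 is the second BrachyGel use.

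**2. Counted days.** Let g be the gap between fractions, 2 to 7 days, with day 0 the first BrachyGel fraction. In both arms the second BrachyGel fraction falls on day 2g.

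| | Formula | g = 2 | g = 7 |
|---|---|---|---|
| Second BrachyGel use | 2g | day 4 | day 14 |
| Counted days after it | 30 − 2g | 26 | 16 |
| Non-serious recording ends, Arm A (last fraction on day 2g) | 2g + 30 | day 34 | day 44 |
| Non-serious recording ends, Arm B (last fraction on day 3g) | 3g + 30 | day 36 | day 51 |

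So 4–14 days (Arm A) or 6–21 days (Arm B) of recorded follow-up lie beyond the counting window. Delays would reduce the cover after the second use further.

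**3. The plan's boundary, reproduced.** Section 10.5 gives p₀ = 0.04, p₁ = 0.09 and α = β = 0.10. Let D = ln(p₁/p₀) + ln[(1−p₀)/(1−p₁)] = 0.8109 + 0.0535 = 0.8644.

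- Intercept = ln[(1−β)/α]/D = 2.1972/0.8644 = 2.54.
- Slope = ln[(1−p₀)/(1−p₁)]/D = 0.0535/0.8644 = 0.062.

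Both constants match section 10.5, although the text attaches the names slope and intercept the wrong way round. Stopping when the count reaches 2.54 + 0.062n, rounded up, gives steps at n = 8, 24 and 40, as in the printed table. The boundary depends only on the two rates and two error levels, so changing the window does not alter it.

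**4. Effect of uncounted events.** The documents do not say what share m of aVAEs starts after the window closes, so m is an assumption. With a true rate of 9%, the counted rate is 0.09 × (1 − m). The chance of crossing the printed table, checked after each participant from the 3rd to the 45th by exact binomial recursion, is:

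| Missed share m (assumed) | Counted rate | Chance of crossing |
|---|---|---|
| 0% | 9.00% | 31.5% |
| 2% | 8.82% | 30.0% |
| 5% | 8.55% | 27.8% |
| 10% | 8.10% | 24.3% |
| 20% | 7.20% | 17.7% |

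At the null rate of 4% with every event counted, it is 2.6%.

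**The case against.** **The label is only a slip.** The governing words are clear: first treatment using BrachyGel. Read as fractions, 2 or 3 is exactly right, and a careful reader would recover the intent. That stands as an explanation of the error. It does not make the sentence correct, and this is the operative definition for a stopping rule.

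**The window is a design choice.** The events are meant to be acute. A fixed 30 days is the same in both arms, settles each participant's status promptly, and still covers the second exposure for 16–26 days. Section 10.1 also notes that the final fraction may involve less therapy, and Arm A's second BrachyGel use is that fraction. All of this is fair. A reader might infer that events after the second exposure are dropped altogether. They are not: at the planned spacing, only those starting more than 16–26 days after it are missed.

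**The loss may be very small.** Nothing in the documents suggests that many packing-related grade ≥3 events start that late. Section 2.3.1 hypothesizes that packing pain resolves within 1 day. At a 2% loss the chance of crossing falls by 1.5 percentage points. This stands, and it is why a range is shown and not a single figure. One can also argue that the 9% refers to the aVAE as defined, window included. The boundary then keeps its planned properties, and the question becomes whether that definition covers the second exposure adequately.

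**Other safeguards exist.** A reader might take the SPRT as the only protection. It is not. The DSMC reviews all adverse events at monthly meetings (11.1.4), serious events reach the coordinating center within 24 hours (9.1.7), device effects posing unreasonable risk lead to termination (9.2.2), and unacceptable risk permits suspension (7.1). Late events remain visible; only the numerical count omits them.

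**Conclusion.** The concern holds in two parts of different weight.

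The period label is wrong. It contradicts sections 4.1, 6.1 and 10.3.2 and, if followed, would exclude Arm B's first-exposure events from the stopping count. This rests on no assumption.

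The window is narrower than the data already collected, leaving 16–26 counted days after the second BrachyGel use. The day count assumes the planned 2–7 day spacing. The effect on the boundary cannot be determined from the documents. Over an assumed loss of 2–20% of events at a true 9% rate, the chance of crossing falls from 31.5% to between 30.0% and 17.7%. The upper end of that range has no support in the text and should not be read as an estimate. Because the rule triggers in fewer than a third of trials at the rate the plan calls unacceptable, even a modest loss is worth avoiding when the remedy is a change of wording.

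**What to change.** - In section 10.5 ii), correct the label to Period 1 or 2 (fraction 2 in Arm B, fraction 3 in Arm A).
- Count BrachyGel-related events from the first BrachyGel fraction to 30 days after the participant's last BrachyGel fraction. At the planned spacing this is 34–44 days in both arms, and it ends no later than the collection period in section 9.1.5. Ending at 30 days after the last study treatment would be less suitable: Arm B's fraction 5 uses standard packing, so its window would run 36–51 days against 34–44 in Arm A.
- Reconcile the start of the window with section 9.1.5, where recording begins only once fraction 2 is completed. As written, an event during Arm B's first BrachyGel fraction falls outside recording, so this part needs a change to collection as well as to the definition.

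**Cost.** A short wording change in two sections. The stopping table stays as printed. The downsides are a slightly higher chance of a precautionary accrual pause and each participant's status being settled 4–14 days later.

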10.4 Sample Size and Accrual

For this crossover study the primary comparison is based upon the 2x2 initial crossover portion. The primary endpoint is the difference of D2cc dosimetry measurements between periods 1 and 2 (fractions 2 and 3) for sequence arm A and sequence arm B based upon a two-sample comparison of the mean difference to the non-inferiority margin. Data from 51 patients treated at UVA with fraction 2 and 3 information, reported overall in Romano et al 2018¹⁹, with standard packing resulted in a mean (standard deviation) of 0.12 (1.56) and 0.10 (0.92) D2cc for the difference for bladder and rectal dosimetry, respectively. The

width of the 95% CI for the mean difference was 0.9 and 0.5 for bladder and rectal dosimetry, respectively. Based upon these measurements and clinical judgement, a non-inferiority margin of δ =(0.12+1.56=1.68) was chosen for this study.

Version Date: 11/16/2021

Justification for the sample size is based upon obtaining sufficient accrual to test the primary hypothesis that use of the hydrogel vaginal packing is non-inferior to standard packing methods in 1) bladder and 2) rectal dosimetry by more than a non-inferiority margin. Let $diff_A$ and $diff_B$ denote the differences between fractions.

The primary hypothesis to be tested is H_o : μ_{diffA} - μ_{diffB} $\geq \delta$ versus H_a : μ_{diffA} - μ_{diffB} $< \delta$, where the non-inferiority margin, δ =1.68, *each* for bladder and rectal, with a one-sided 2.5% level t-test. A sample size of 20 evaluable cervical cancer participants per arm achieves 94% power to detect non-inferiority using a one-sided t-test when the margin of non-inferiority is 1.68, the true difference between the means and the reference (standard) value is 0.12, and the assume population standard deviation is 1.56. Power is 96% if one uses the estimates for rectal dosimetry.

Adjusting for participants not satisfying the evaluable criteria (*section 10.3.1*), it is estimated that approximately 57 cervical cancer participants will need to be accrued to the study in order to test the primary study hypothesis. Each site may allow up to 10 oncologist and 4 physicists/dosimetrist to participate in completing the Physician and Physicist Assessments.

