11.1.4 Safety Oversight

The University of Virginia Cancer Center Data and Safety Monitoring Committee (CC DSMC) will provide oversight of the conduct of this study. The CC DSMC will report to the UVA Protocol Review Committee (PRC).

The UVA CC DSMC will review the following:

- All adverse events
- Audit results
- Application of study designed stopping/decision rules
- Whether the study accrual pattern warrants continuation/action
- Protocol violations

The UVA CC DSMC will meet every month for aggregate review of data. Tracking reports of the meetings are available to the PI for review. Issues of immediate concern by the DSMC are brought to the attention of the sponsor (and if appropriate to the PRC and IRB) and a formal response from the sponsor is requested. Per the UVA Cancer Center NIH approved institutional plan, this study will be audited approximately every 6 months. The audit may include direct access to source data/documents.

Any study under the purview of the University of Virginia IRB-HSR is subject to review of files at the University of Virginia. Studies are chosen for Post-approval Monitoring either a) at random or b) requested by a study team member or any member of the IRB-HSR.

The purpose of Post-approval Monitoring audits is to ensure that documentation of clinical research studies is of the highest quality, verify protocol adherence, and ensure that all Federal and local rules concerning clinical research are being fulfilled. Post-approval monitoring is done by staff within the office of the Vice President for Research (VPR) in accordance with their Standard Operating Procedures. The conduct of an on-site review may include but is not limited to:

- requests for progress reports from investigators,
- examinations of research records, including signed informed consent documents, protocol modifications, and unexpected, serious, and/or related adverse experience reports,
- contacts with research subjects, or
- observation of the consent process and/or research procedures. Examples of when observation of the consent process could occur are:

 Full board IRB determines during review of a project that a conflict of interest exists such that the informed consent process should be observed by a neutral party;

Version Date: 11/16/2021

- IRB is made aware of a complaint or concern with regard to the informed consent process; or

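### Section 10.5 swaps the slope and intercept of its safety stopping line, quotes 10%/10% errors that the rule in use does not deliver, and prints no bound beyond 45 of about 57 participants

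*Combined protocol and SAP*

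**What the plan says.** Section 10.5 (Safety Monitoring) specifies that "the upper boundary of a sequential probability ratio test (SPRT) based upon a binomial test of proportions for aVAE will be used for monitoring". The test contrasts an acceptable rate of 4% with an unacceptable rate of 9%, "with nominal type I and II errors of 10% and 10%, respectively". It then gives the line: "The slope of the parallel line for monitoring is 2.54 and the intercept is 0.062".

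The table that follows is indexed by the number of participants who have received BrachyGel:

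- 3 to 7 exposed: 3 or more events
- 8 to 23 exposed: 4 or more
- 24 to 39 exposed: 5 or more
- 40 to 45 exposed: 6 or more

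The table ends there. Crossing a bound suspends accrual until the PI, co-investigators and DSMC have reviewed the data. Section 10.4 states that "approximately 57 cervical cancer participants will need to be accrued". Section 2.3.2 has both arms receiving BrachyGel, and section 10.5 covers all treated participants, not only the 40 evaluable ones.

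The event window runs from the first fraction given with BrachyGel, glossed as "ie. Period 2 or 3 depending on the randomization arm". Under section 11.1.4 the DSMC's review includes "Application of study designed stopping/decision rules".

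**The concern.** Four things look wrong.

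1. A slope of 2.54 events per participant cannot be right for event rates of 4% to 9%.
2. The 10%/10% errors are design inputs of a sequential test with both boundaries and no sample-size limit. Dropping the lower boundary and ending at a few dozen participants changes both error rates. The plan gives no actual stopping probability.
3. The table ends at 45, although about 57 participants are to be accrued.
4. The period gloss does not match the plan's own numbering of fractions and periods.

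This section holds the plan's numerical stopping bound for a device that section 2.2.5 says has not been used in living humans. A DSMC or IRB member reading it sees a 10% type II error and would reasonably take the rule to stop about 90% of the time at the unacceptable rate. Anyone who tried to extend the table from the printed sentence would get a line that can never be crossed.

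**Working it through.** **Inputs (section 10.5):** p0 = 0.04, p1 = 0.09, α = β = 0.10; upper boundary only; printed table to 45. **Section 10.4:** accrual of about 57.

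**The line (Wald's binomial formulas).**

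- D = ln[p1(1−p0) / (p0(1−p1))] = ln[(0.09 × 0.96)/(0.04 × 0.91)] = 0.8644
- slope = ln[(1−p0)/(1−p1)]/D = ln(0.96/0.91)/0.8644 = 0.0619
- upper intercept = ln[(1−β)/α]/D = ln(9)/0.8644 = 2.542

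Both printed numbers are reproduced, but each carries the other's label. Read literally, the line is 0.062 + 2.54n, which requires 2.6, 5.1 and 7.7 events at n = 1, 2 and 3. That is always more events than participants.

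**The table.** The bound is the smallest whole number at or above 2.542 + 0.0619n. The line is 3.037 at n = 8, 4.027 at n = 24, 5.017 at n = 40 and 6.007 at n = 56, so the bound steps up at those four points. The first three match the printed rows exactly. The rounded values 2.54 and 0.062 give the same steps. The same line therefore gives 6 or more for 46 to 55 and 7 or more for 56 to 57.

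**Actual stopping probabilities.** These come from an exact binomial recursion, participant by participant from n = 3, counting a path as stopped when it first reaches the bound:

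| True rate | Printed table, to 45 | Same line, to 50 | Same line, to 57 |
|---|---|---|---|
| 4% | 2.6% | 3.0% | 3.5% |
| 9% | 31.5% | 35.9% | 42.0% |
| 12% | 56.4% | 62.4% | 69.5% |
| 15% | 76.4% | 81.8% | 87.1% |
| 20% | 93.8% | 96.2% | 97.9% |

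At 9% the chance of not stopping is 100 − 31.5 = 68.5% (to 45) or 100 − 42.0 = 58.0% (to 57), against a nominal 10%. Stopping reaches 90% only at a true rate of 18.4% (to 45) or 15.8% (to 57).

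**Where the nominal figures do apply.** The open-ended test with two boundaries crosses the upper one with probability 7.6% at 4% and 90.1% at 9%. It needs on average 99 and 83 participants respectively. The upper boundary alone needs about 225 participants to reach 90% at 9%.

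**Uncovered participants.** At most 57 − 45 = 12. The documents do not give the number who will be exposed, so the range is 0 to 12.

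**Period wording.** Section 10.3.2 defines "periods 1 and 2 (fractions 2 and 3 under the 2x2 crossover structure". Section 6.1 states: "For Arm B of the study, the BrachyGel Packing System will be used during fractions 2 and 4". It places Arm A's first use at fraction 3. First use is therefore period 1 (Arm B) or period 2 (Arm A), whereas section 10.5 says period 2 or 3. Those numbers fit fractions, not periods.

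**The case against.** The strongest reply is that the plan discloses most of this. It says only the upper boundary is used, calls the errors nominal, and attaches them to the test that generated the line. It never promises 90% stopping at 9%. That is fair, and the full test does have roughly those properties. It still leaves the reader without any actual stopping probability, and 58% to 68% cannot be inferred from a stated 10%.

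Second, the text does not say that monitoring ends at 45; that is read from the table. With the labels corrected the line covers any number, which is why both readings are shown. At 9% the result is 31.5% or 42.0%, and neither is near 90%.

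Third, 12 uncovered participants is a maximum. Suppose the 57 − 40 = 17 non-evaluable participants split evenly between arms and all fail for having fewer than three fractions. The Arm A half (about 8.5) would never receive BrachyGel, leaving about 48 to 49 exposed and a gap of 3 to 4. From 46 to 55 the derived bound equals the last printed row, so a new number is needed only at 56 to 57. This reduces the practical effect but does not justify an unexplained end to the table.

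Fourth, the label swap is evident on reading and changes no printed bound, and the period gloss sits beside operative words that are clear. Both points stand; these are wording errors.

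Finally, the bound is not the only protection. Monthly DSMC review of all adverse events (11.1.4), 24-hour SAE reporting (9.1.7), device-effect termination deadlines (9.2.2), suspension for unacceptable risk (7.1) and individual discontinuation criteria (7.2) all operate independently. The type I departure is in the conservative direction.

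**Conclusion.** The concern holds and should be fixed. The slope and intercept are certainly reversed, with no effect on the bounds for 3 to 45. The quoted type II error of 10% is about 58% to 68% for the rule actually used, depending on whether the line continues to 57 or ends at 45. The type I error is about 2.6% to 3.5%, not 10%. Between 0 and 12 exposed participants have no printed bound. The period gloss contradicts the numbering elsewhere, as wording only.

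The stopping probabilities assume independent participants with a common event rate and a count checked after each participant. The conclusion does not depend on which end point is taken. Because other oversight runs in parallel, the defect is one of correction and disclosure, not an absence of safety monitoring.

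**What to change.** In section 10.5:

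- Swap the labels, so that the slope is 0.062 and the intercept 2.54.
- Extend the table to every participant who may be exposed, using the plan's own line (6 or more for 46 to 55, 7 or more for 56 to 57), or state why it ends at 45.
- Report the rule's actual stopping probabilities beside or in place of the nominal errors. To 57 these are about 3.5% at 4%, 42% at 9%, 87% at 15% and 98% at 20%.
- Reconcile the first-use parenthetical with the period and fraction numbering in sections 3, 6.1 and 10.3.2.

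The cost is a text and table edit. Existing bounds for 3 to 45 do not change. The stated operating characteristics become less favourable, and the edit does little to raise sensitivity at 9%. It does let the DSMC and IRB judge whether that sensitivity is acceptable.
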